6.3.2. Clinical Study Material Administration

Each participant will receive 2 doses of IP by IM injection approximately 8 weeks apart (Day 1 and Day 57) in Part 1 and Part 2 of study. The IM injections will be administered into the anterolateral thigh, according to their assigned regimen and according to the procedures specified in the mRNA-1273-P206 Pharmacy Manual.

At each visit when IP is administered, participants will be monitored for a minimum of 60 minutes after administration in Part 1 and 30 minutes after administration in Part 2. Assessments will include body temperature measurements (must be measured via the axillary route and any axillary reading of $\geq 37.8^{\circ}\text{C}/\geq 100^{\circ}\text{F}$ may be confirmed by a rectal measurement) and monitoring for local or systemic reactions.

Eligibility for the subsequent dose of IP will be determined by the criteria outlined in Section 7.

The study sites will be appropriately staffed with individuals with basic pediatric cardiopulmonary resuscitation training/certification. Either on-site resuscitation equipment and

Protocol: mRNA-1273-P206, Original

personnel or appropriate protocols for the rapid transport of participants to a resuscitation area or facility are required.

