8.7. Study Vaccine Administration

A single injection (mRNA-1273.214 or placebo) will be administered to all participants on dosing visits as described in the SoA (Table 1).

After completing all prerequisite procedures prior to vaccination, the study vaccine will be administered via IM injection into the anterolateral thigh. Additional details regarding vaccine administration procedure are provided in Section 6.3.2.

The participants will be observed closely (via clinical assessment including measurement of vital signs if clinically indicated based on discretion of the investigator) for at least 60 minutes (Part 1) or 30 minutes (Part 2) following the administration of the vaccine, with appropriate medical treatment readily available in case of anaphylaxis or other hypersensitivity reactions.

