8.10.2. Use of Electronic Diaries

At the time of consent, participants' parent(s)/LAR(s) must confirm they will be willing to complete an eDiary using either an application downloaded to their smartphone or using a device that is provided at the time of enrollment. Before enrollment on Day 1, participants' parent(s)/LAR(s) will be instructed to download the eDiary application or will be provided an eDiary device to record solicited ARs (Section 8.11.3) on Day 1. Based on availability, smartphone devices may be provided to those participants' parent(s)/LAR(s) who do not have their own device to use for eDiary activities.

At each injection visit, participants' parent(s)/LAR(s) will be instructed (Day 1) or reminded (Day 57) on thermometer (axillary and rectal) usage to measure body temperature, ruler usage to measure injection site erythema and swelling/induration (hardness), and assessment for localized axillary swelling or tenderness on the same side as the injection arm/thigh.

At each injection visit, participants' parent(s)/LAR(s) will record data into the eDiary starting approximately 30 minutes after injection under the supervision of the study site staff to ensure successful entry of assessments. The study site staff will perform any retraining as necessary. Participants' parent(s)/LAR(s) will continue to record data in the eDiary after they leave the study site, preferably in the evening and at the same time each day, on the day of injection and for 6 days following injection.

Participants' parent(s)/LAR(s) will record the following data in the eDiary:

Solicited local and systemic reactogenicity ARs, as defined in Section 8.11.3, that occur
on the day of each vaccine administration and during the 7 days after vaccine
administration (ie, the day of injection and 6 subsequent days). Capturing details of ARs
in the eDiary should not exceed 7 days after each vaccination. If a solicited local or

Protocol: mRNA-1273-P206, Original

systemic AR continues beyond Day 7 after vaccination, the event should be reviewed by the study site staff either via a telemedicine visit/call or at an unscheduled study site visit.

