- Body temperature measurement should be performed at approximately the same time each day using the thermometer provided by the study site. If body temperature is taken more than once in a given day, only the highest temperature reading should be recorded. Body temperature must be measured via the axillary route and any axillary reading of ≥ 37.8°C/≥ 100°F may be confirmed by a rectal measurement.
- Measurement, as applicable, for solicited local ARs (injection site erythema and swelling/induration); the size measurements will be performed using the ruler provided by the study site.
- Any medications taken to treat or prevent pain or fever on a day of injection or for the next 6 days.

The eDiary will be the only source document allowed for solicited systemic or local ARs (including body temperature measurements). Participants' parent(s)/LAR(s) will be instructed to complete eDiary entries daily. Quantitative temperature recordings and measurement of any injection site erythema or swelling/induration reported on the following day may be excluded from the analyses of solicited ARs.

Study site staff will review eDiary data with participants' parent(s)/LAR(s) at telemedicine visits 7 days after each injection in both Part 1 and Part 2. eDiary data will also be reviewed during the additional visits 3 days after each injection (ie, on Day 4 and Day 60) in Part 1 only.

The eDiary will be used every 4 weeks, starting at Day 99 through Day 211 and every 8 weeks, starting at Day 265 through Day 377, to capture the occurrence of AEs, MAAEs, SAEs, AESIs, or AEs leading to withdrawal. As specified in the SoA (Table 1), the eDiary will prompt the participant's parent(s)/LAR(s) to complete an eDiary questionnaire that collects the following data:

- Changes in health since last completing the questionnaire or since in contact with the study site
- Any MAAEs, AESIs, or SAEs
- Known close contact with someone in the household who has known COVID-19 or SARS-CoV-2 infection. An infected person can spread SARS-CoV-2 starting 2 days before they have any symptoms (or, for asymptomatic people, 2 days before the positive specimen collection date) through 10 days after symptom onset (or, for asymptomatic

Protocol: mRNA-1273-P206, Original

people, 10 days after positive test). Per the CDC, "close contact" to someone with COVID-19 is defined as follows:

- o Being within 6 feet for a total of 15 minutes or more
- o Providing care at home

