8.11.3. Solicited Adverse Reactions

The term "reactogenicity" refers to the occurrence and intensity of selected signs and symptoms (ARs) that occur after IP injection. The eDiary will solicit daily participant reporting of ARs using a structured checklist (Section 8.10.2). Participant's parent(s)/LAR(s) will record such occurrences in an eDiary on the day of each dose of injection and for the 6 days after the day of dosing.

Severity grading of reactogenicity will occur automatically based on participant entry into the eDiary according to the grading scales presented in Table 7, modified from the Toxicity Grading Scale for Healthy Adult and Adolescent Volunteers Enrolled in Preventative Vaccine Clinical Trials (DHHS 2007).

Capturing details of ARs in the eDiary should not exceed 7 days after each vaccination. If a solicited local or systemic AR continues beyond Day 7 after vaccination, the event should be reviewed by the study site staff either via a telephone call or an unscheduled study site visit. All solicited ARs (local and systemic) will be considered related to the IP. If a participant's parent(s)/LAR(s) reported a solicited AR during the solicited period and did not record the event in the eDiary, the event should be recorded on the Reactogenicity page of the eCRF. If the event starts during the solicited period, but continues beyond 7 days after dosing, the participant's parent(s)/LAR(s) should notify the site to provide an end date to close out the event on the Reactogenicity page of the eCRF. If the participant's parent(s)/LAR(s) reported an event after the solicited period (ie, after Day 7), it should be recorded as an AE on the AE page of the eCRF.

Table 7: Solicited Adverse Reactions and Grades: Age 12 Weeks to < 6 Months

Reaction	Grade 0	Grade 1	Grade 2	Grade 3	Grade 4 ¹
Local Reaction					
Injection site pain/tenderness	None	Mild discomfort to touch or some pain but no interference with normal daily activities	Cries when limb is moved/refuses to move limb or pain interferes with normal daily activities	Significant pain at rest or pain prevents normal daily activities	Requires emergency room visit ² or hospitalization
Injection site erythema (redness)	< 5 mm/ < 0.5 cm	5-20 mm/ 0.5-2.0 cm	> 20-50 mm > 2.0-5.0 cm	> 50 mm/ > 5 cm	Necrosis or exfoliative dermatitis
Injection site swelling/induration (hardness)	< 5 mm/ < 0.5 cm	5-20 mm/ 0.5-2.0 cm	> 20-50 mm > 2.0-5.0 cm	> 50 mm/ > 5 cm	Necrosis

Protocol: mRNA-1273-P206, Original

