Reaction	Grade 0	Grade 1	Grade 2	Grade 3	Grade 4 ¹
Groin or underarm swelling or tenderness ipsilateral to the side of injection	None	Some swelling or tenderness but no interference with normal daily activities	Swelling or tenderness that interferes with normal daily activities	Swelling or tenderness that prevents normal daily activities	Emergency room visit ² or hospitalization
Systemic Reaction					
Fever	< 38.0°C	38.0-38.4°C 100.4-101.1°F	38.5-39.5°C 101.2-103.1°F	39.6-40.0°C 103.2-104.0°F	> 40.0°C > 104.0°F
Irritability/crying	None	Lasting < 1 hour or easily consolable	Lasting 1 to 3 hours or requiring increased attention	Lasting > 3 hours or inconsolable	Requires emergency room visit ² or hospitalization
Sleepiness	None	Sleepier than usual or less interested in surroundings	Not interested in surroundings or sleeps through meals	Sleeps most of the time, hard to arouse	Inability to arouse
Loss of appetite	None	Eating less than normal for 1-2 feeds/meals	Missed 1-2 feeds/ meals completely	Missed > 2 feeds/meals completely or refuses most feeds/meals	Requires emergency room visit ² or hospitalization

Abbreviations: AE = adverse event; eCRF = electronic case report form.

Note: Events listed above but starting > 7 days post-study injection will be recorded on the AE page of the eCRF. Causality for each event will be determined per assessment by the investigator.

Source: Guidance for Industry: Toxicity Grading Scale for Healthy Adult and Adolescent Volunteers Enrolled in Preventative Vaccine Clinical Trials (DHHS 2007).

Any solicited AR that meets any of the following criteria must be entered into the participant's source document and must also be recorded by the study site staff on the solicited AR page of the participant's eCRF:

- Solicited local or systemic AR that results in a visit to an HCP (otherwise meets the definition of an MAAE)
- Solicited local or systemic AR leading to the participant withdrawing from the study or the participant being withdrawn from the study by the investigator (AE leading to withdrawal)
- Solicited local or systemic AR lasting beyond 7 days after injection

^{1.} Grading for Grade 4 events per investigator assessment (with exception of fever).

^{2.} Emergency room visit includes urgent care visit.

Protocol: mRNA-1273-P206, Original

• Solicited local or systemic AR that leads to participant withdrawal from IP

• Solicited local or systemic AR that otherwise meets the definition of an SAE

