6.3.2. Solicited Adverse Reactions

An AR is any AE for which there is a reasonable possibility that the test product caused the AE. The term "Solicited Adverse Reactions" refers to selected signs and symptoms occurring after injection administration during a specified post-injection follow-up period (day of injection and 6 subsequent days). The solicited ARs are recorded by the subject in eDiary. The occurrence and intensity of selected signs and symptoms is actively solicited from the participant during a specified post-injection follow-up period (day of injection and 6 subsequent days), using a pre-defined checklist (i.e., solicited ARs).

The following local ARs will be solicited by the eDiary: pain/tenderness at injection site, erythema (redness) at injection site, swelling/induration (hardness) at injection site, and groin or underarm swelling or tenderness ipsilateral to the side of injection.

The following systemic ARs will be solicited by the eDiary: fever, irritability/crying, sleepiness, and loss of appetite.

The AR categories are presented in Table 7 in the protocol.

The solicited ARs will be graded based on the grading scales presented in Table 7 in the protocol, modified from the Toxicity Grading Scale for Healthy Adult and Adolescent Volunteers Enrolled in Preventative Vaccine Clinical Trials (DHHS 2007). Investigator will assess Grade 4 events (with exception of fever).

If a solicited local or systemic AR continues beyond 7 days post injection, the participant's parent(s)/ LAR(s) should notify the site to provide an end date to close out the event on the reactogenicity page of the eCRF.

All solicited ARs (local and systemic) will be considered causally related to injection.

Analyses of solicited ARs will be provided by study part and treatment group for each injection (first or second) based on the associated subset of Solicited Safety Set, i.e. First (Second) Injection Solicited Safety Set, unless otherwise specified.

The number and percentage of subjects who reported each individual solicited local AR (has a toxicity grade of Grade 1 or greater) and solicited systemic AR (has a toxicity grade of Grade 1 or greater) during the 7-day follow-up period after each injection will be tabulated by vaccination group, toxicity grade, and injection (i.e., first or second injection). The number and percentage of subjects who reported each individual solicited AR will also

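### The parent instruction in Protocol Section 8.10.2 names only the armpit, although injections go into the thigh and the solicited reaction is groin or underarm, so groin reactions may be under-ascertained

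*Protocol*

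**What the plan says.** Three parts of the plan bear on this.

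- **Parent instruction.** Protocol Section 8.10.2 says that at each injection visit "participants' parent(s)/LAR(s) will be instructed (Day 1) or reminded (Day 57) on thermometer (axillary and rectal) usage", on using a ruler for redness and swelling at the injection site, and on "assessment for localized axillary swelling or tenderness on the same side as the injection arm/thigh".
- **Injection site.** Protocol Section 6.3.2 states: "The IM injections will be administered into the anterolateral thigh". Section 8.7 agrees: "the study vaccine will be administered via IM injection into the anterolateral thigh". The synopsis gives the same site. None of these offers the arm as an alternative.
- **Solicited reaction.** Protocol Table 7 (Section 8.11.3) lists "Groin or underarm swelling or tenderness ipsilateral to the side of injection" among the local reactions. SAP Section 6.3.2 lists "groin or underarm swelling or tenderness ipsilateral to the side of injection" among the items that the eDiary solicits.

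On capture, Protocol Section 8.11.3 says: "The eDiary will solicit daily participant reporting of ARs using a structured checklist". Section 8.10.2 adds: "The eDiary will be the only source document allowed for solicited systemic or local ARs".

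**The concern.** Section 8.10.2 teaches parents three skills. Two match the items they serve: the thermometer serves fever, and the ruler serves redness and swelling at the injection site. The third does not. It sends the parent to the armpit and refers to an injected arm or thigh, in a trial that injects only the thigh and solicits the groin as well as the underarm.

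Regional swelling or tenderness in an infant who cannot speak has to be looked for. A parent who was shown only the armpit may answer a groin-or-underarm question without having examined the groin.

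The item is one of four solicited local reactions in the primary safety endpoint of both parts. SAP Section 6.3.2 tabulates each of them separately by grade and by injection, so a shortfall would appear in a reported row. Grade 3 or higher solicited local reactions lasting at least 24 hours also count towards pause rule 2 (Protocol Section 7.4, Table 4).

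**Working it through.** The plan has no figure to reproduce here. The check is a comparison of texts, followed by a look at which capture routes could make good an omission.

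**Step 1: compare the sites.**

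- Where the vaccine goes: anterolateral thigh only (Protocol synopsis, Sections 6.3.2 and 8.7).
- What is solicited: groin or underarm, on the injected side (Protocol Table 7; SAP Section 6.3.2).
- What parents are taught to assess: axilla only (Protocol Section 8.10.2).

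The instruction covers one of the two solicited sites. Its mention of the arm does not fit the stated injection site.

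**Step 2: ask whether another route supplies the groin.**

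- *The checklist and the cross-reference.* Section 8.10.2 sends parents to the definitions in Section 8.11.3, and the SAP confirms that the diary item names the groin. This prompts the question each day but does not describe how to examine for the sign.
- *The supervised first entry.* Staff oversee it about 30 minutes after injection and retrain if needed. The groin is not mentioned there either.
- *The eDiary review.* Staff go through the entries with parents 7 days after each dose by telemedicine. The extra clinic visits on Days 4 and 60 are in Part 1 only, with symptom-directed examination. The injection-site examination in the Schedule of Assessments footnote concerns the injection site.
- *The Reactogenicity page of the eCRF.* It takes events that a parent reported but did not enter. It cannot take an event that nobody noticed.

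These routes reduce the risk. None reliably recovers a groin reaction that was not looked for.

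**Step 3: what pause rule 2 needs.** The rule requires at least 2 participants and at least 5% of those dosed in the arm, so the count needed is the larger of 2 and 0.05 × n rounded up.

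- Full Part 1 arm, n = 50: 0.05 × 50 = 2.5, so 3 participants.
- Part 1 Arm 2 as reported in SAP Section 7, n = 18 (taking all 18 as dosed): 0.9, so the floor of 2 applies.
- Planned Part 2 arm, n = 300: 0.05 × 300 = 15 participants.

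In Part 1 the counts are small enough for one missed qualifying event to matter in principle. Against that, Table 7 defines Grade 3 for this item by swelling or tenderness that stops normal daily activities. Such an event is harder to overlook than a Grade 1 event, so the milder grades are the more exposed.

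**Step 4: can the shortfall be sized?** It would need the true rate of groin reactions after thigh injection at 12 weeks to < 6 months, and the fraction that parents miss with and without groin instruction. The documents give none of these.

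**The case against.** The strongest reply is that the instrument parents use every day already names the groin. The solicited item is correct in Table 7 and in the SAP, and Section 8.10.2 itself points to that definition. On this view the axillary phrase is generic wording carried into a summary sentence, much as the blinding text in Section 6.2 speaks of an arm or leg. The training sheets and eDiary screens are not part of the documents and may well show the groin. This stands as far as it goes: it makes under-ascertainment a possibility and not an established result. It does not remove the inconsistency, because the only instruction described leaves out the site nearer the injection.

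A reader might infer more than the text supports, in four ways.

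- *That groin reactions will be under-reported.* The checklist, staff review and eCRF page make this unproven.
- *That parents are sent to the wrong site.* Underarm is half of the solicited item, so the instruction is incomplete.
- *That the loss can be sized from Study mRNA-1273-P204.* Protocol Section 2.3.2 reports injection site lymphadenopathy of 1.4% against 0.2%. Those are unsolicited events after a different vaccine (mRNA-1273) in children aged 6 months to < 2 years, and the documents do not give that study's injection site. They are not rates for this solicited item.
- *That a planned vaccine–placebo comparison is biased.* If both blinded arms miss the same fraction m, each rate is multiplied by (1 − m). The absolute difference shrinks by that factor and the ratio is unchanged. But no test or difference is planned for this item. Solicited reactions are summarised descriptively, with confidence intervals only for any local, any systemic and any solicited reaction. The placebo arm exists only in Part 2, and SAP Section 7 reports that enrollment was paused with 18 participants in Part 1 Arm 2.

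**Conclusion.** The point holds as an inconsistency in an operative instruction, with a possible effect on ascertainment. The conclusion assumes that sites train parents as Section 8.10.2 is written. If the training material already covers the groin, only the protocol wording is at fault.

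The direction of any error would be downward, mainly in the milder grades. Its size is unknown and should not be given a number. The correction is worth making because the eDiary is named as the source for these reactions, the item is part of the primary safety endpoint and of a pause rule, and the change is almost free.

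**What to change.** In Protocol Section 8.10.2, replace the axillary phrase with wording that matches Table 7: groin or underarm swelling or tenderness, on the side of the injected thigh. Drop the reference to an injected arm. Use the same wording in the parent training material and the Day 57 reminder, and check that the eDiary screen agrees.

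The cost is one sentence and one training sheet. The endpoint, the grading scale, the pause rule and the SAP stay as they are. For infants already dosed, a short note of what parents were actually shown would tell readers how to interpret this row of the reactogenicity tables.

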3. OBJECTIVES AND ENDPOINTS

The objectives that will be evaluated in this study and endpoints associated with each objective are provided in Table 2 (Part 1) and Table 3 (Part 2).

Table 2: Objectives and Endpoints for Part 1

Objectives	Endpoints		
Primary Objectives	Primary Endpoints		
• To evaluate the safety and reactogenicity of 2 dose levels¹ of mRNA-1273.214 vaccine administered as 2 doses 8 weeks apart in participants aged 12 weeks to < 6 months	 Solicited local and systemic ARs through 7 days after each injection Unsolicited AEs through 28 days after each injection MAAEs throughout the entire study period SAEs throughout the entire study period AESIs throughout the entire study period AEs leading to discontinuation from study participation postdose throughout the entire study period 		
Secondary Objectives	Secondary Endpoints		
• To evaluate the immunogenicity of 2 dose levels¹ of mRNA-1273.214 vaccine administered as 2 doses 8 weeks apart in participants aged 12 weeks to < 6 months	GMT of antibodies against SARS-CoV-2 VOC (Omicron) at 28 days after second dose		

Abbreviations: AE = adverse event; AESI = adverse event of special interest; AR = adverse reaction; GMT = geometric mean titer; MAAE = medically attended adverse event; mRNA = messenger RNA; SAE = serious adverse event; SARS-CoV-2 = severe acute respiratory syndrome coronavirus 2; VOC = variants of concern.

¹ Dose levels of mRNA-1273.214 vaccine administered to participants will be 5 μg and 10 μg.

Protocol: mRNA-1273-P206, Original

Table 3: Objectives and Endpoints for Part 2

Objectives	ndpoints		
Primary Objectives	Primary Endpoints		

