6.3.3. Physical Examinations and Vital Signs

Vital signs, including length/height, weight, and body temperature (via axillary route) will be presented in a listing.

Abnormal physical examination findings will be reported on the medical history or adverse events eCRF, as appropriate.

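### Fever is graded from 38.0°C with no route stated, while rectal confirmation is optional and only the day's highest reading is kept, so absolute fever rates and grades depend partly on how often parents re-measure

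*Protocol*

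**What the plan says.** Protocol section 3 (Tables 2 and 3) lists "Solicited local and systemic ARs through 7 days after each injection" as a primary safety endpoint in both parts. SAP 6.3.2 names the components: "The following systemic ARs will be solicited by the eDiary: fever, irritability/crying, sleepiness, and loss of appetite".

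Measurement is set in Protocol 8.10.2: "Body temperature must be measured via the axillary route and any axillary reading of ≥ 37.8°C/≥ 100°F may be confirmed by a rectal measurement". The same rule appears in the Schedule of Assessments notes and in 6.3.2, 7.1.1 and 8.6. For the diary, 8.10.2 adds: "If body temperature is taken more than once in a given day, only the highest temperature reading should be recorded".

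Grading is set in Protocol 8.11.3: "Severity grading of reactogenicity will occur automatically based on participant entry into the eDiary". In Table 7, Grade 1 fever is "38.0-38.4°C 100.4-101.1°F", and no fever grade names a route. A Table 7 footnote leaves Grade 4 to the investigator for every reaction except fever, so fever is graded on the number alone.

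SAP 6.3.2 refers back to Table 7 and adds no route rule. The SAP mentions route only in 6.3.3, for vital signs: "body temperature (via axillary route) will be presented in a listing".

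**The concern.** The axillary trigger of 37.8°C lies below the 38.0°C at which fever starts, so the protocol itself treats an axillary reading just under 38.0°C as worth checking. The check is left to the parent, and its result goes onto the same scale as an unchecked axillary reading. Two infants with the same temperature can therefore receive different grades because one parent took a second reading.

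Fever matters here more than most solicited reactions. Protocol 2.2 singles it out as the exception to an otherwise consistent reactogenicity profile in children aged 6 months to under 6 years. Protocol 2.3.2 reports one related serious event in the youngest group of the earlier pediatric study, a fever with febrile seizure. The Part 1 results decide the Part 2 dose, and Grade 3 or higher systemic reactions feed pause rule 3 in Table 4. If the recorded rate mixes two routes in unknown proportions, its absolute level and grade mix are hard to interpret or to compare with other studies. If only the highest value is stored, without route, the analysis cannot separate them afterwards.

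**Working it through.** The documents give no fever rate, no axillary-rectal offset and no re-measurement rate, so there is no planned figure to reproduce. The check has a textual part and an illustrative part.

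**Reading the rules together, for one infant on one day**

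- Highest axillary reading below 37.8°C: no rectal check is prompted. Grade 0.
- Highest axillary reading 37.8-37.9°C, parent stops: Grade 0.
- Same reading, parent takes a rectal reading of 38.0°C or more: the higher value is entered and graded 1 or above.
- Highest axillary reading 38.0°C or more: already fever. A higher rectal reading can raise the grade. A lower one changes nothing if the highest-reading sentence is taken literally.

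Any-grade fever therefore depends on re-measurement only in the 37.8-37.9°C band. The grade mix can also shift above it.

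**Illustration of size (all inputs are assumptions)**

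Recorded any-grade fever = p0 + b × c × r, where

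- p0 = share with highest axillary reading ≥ 38.0°C
- b = share with highest axillary reading 37.8-37.9°C
- c = chance that a rectal reading is ≥ 38.0°C in that band
- r = share of triggered readings that are re-measured

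To obtain p0, b and c, I simulated a rectal daily maximum with SD 0.5°C and an axillary reading 0.5°C lower on average with SD 0.2°C. Values were rounded to 0.1°C and the higher one kept when re-measured. With r going from 0 to 1:

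| Assumed mean rectal maximum | p0 (r = 0) | p0 + b × c (r = 1) | Grade 2 or higher, r = 0 to r = 1 |
|---|---|---|---|
| 37.3°C | 1.6% | 1.6 + 2.3 × 0.90 = 3.7% | 0.1% to 1.0% |
| 37.5°C | 3.9% | 3.9 + 4.3 × 0.92 = 7.9% | 0.4% to 2.7% |
| 37.9°C | 15.4% | 15.4 + 10.4 × 0.96 = 25.4% | 2.6% to 13.0% |

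The offset matters too. At a mean of 37.9°C, any-grade fever goes from 32.1% to 41.5% with an offset of 0.2°C, and from 5.7% to 11.4% with 0.8°C. In a Part 2 arm of about 300, the middle row is 300 × 0.039 ≈ 12 infants against 300 × 0.079 ≈ 24.

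**Between-group comparison**

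With the same temperatures in both groups, the artificial difference is b × c × (r1 − r2). It is zero when re-measurement is equally common. If it were 75% in one group and 25% in the other, with b = 5% and c = 0.9, it would be 0.05 × 0.9 × 0.5 = 2.25 percentage points.

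**Small numbers and pause rule 3**

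SAP section 7 bases the Part 1 Arm 2 interim analysis on 18 infants, so one reclassified infant moves the fever rate by 1/18 = 5.6 points. Pause rule 3 needs at least 2 participants and at least 5% of an arm: 3 of 50 or 15 of 300. Its input can shift with re-measurement, but it concerns Grade 3 or higher (39.6°C and above for fever) lasting at least 24 hours. Such readings are very rare in the model above, so this link is a matter of principle.

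**The case against.** Several objections have force.

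- **Part 2.** A reader might infer that mixed routes blur or bias the vaccine-placebo comparison. The documents do not support that. Part 2 is randomized and observer-blind, so re-measurement should be similarly common in both arms. Fever carries no hypothesis test. In the 37.9°C illustration 46.0% of infants have a rectal maximum of 38.0°C or more, so re-measurement moves the recorded rate (15.4% to 25.4%) towards the rectal one.
- **Part 1.** A reader might infer that open-label parents bias the dose choice. Both arms receive active vaccine, and nothing indicates that parents at 5 µg and 10 µg would re-measure differently. The dose choice also rests on overall safety and immunogenicity. Differential re-measurement is possible there, but not shown.
- **A rectal reading can never lower a grade.** This follows from a literal reading of the highest-reading sentence. That sentence may be meant for repeat readings over the day, with the confirming reading governing. The documents leave this open.
- **Route is not captured.** The eDiary specification and the eCRF are not among the documents. Only the silence of the protocol and SAP can be stated.
- **Axillary-only as the main result.** This would buy uniformity at the price of sensitivity in a safety endpoint. It is a debatable preference, so the planned fever table should stay.

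What stands is that the written plan yields a mixed-route rate, and that neither document provides for separating the routes.

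**Conclusion.** The point holds as one about the absolute fever rate and the grade mix. Following the protocol and SAP as written, both depend partly on how many parents take an optional second reading, and neither document identifies the governing reading or provides for recording or analysing route. For any-grade fever the dependence is confined to highest axillary readings of 37.8-37.9°C; grades can also move above that.

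The direction comes from the text. The size does not: it ranges from about 2 to about 10 percentage points across the assumed mean temperatures at a 0.5°C offset, and the highest row assumes that nearly half of infants reach 38.0°C rectally. No between-arm bias is claimed for Part 2 and none is demonstrated for Part 1. The matter deserves correction because the endpoint is primary and the remedy is cheap.

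**What to change.** - **Protocol 8.10.2 and 8.11.3:** reconcile the rectal-confirmation sentence with the highest-reading sentence by stating which reading is graded. Have the eDiary store the axillary reading and any rectal reading as separate entries, each with its route. A route flag on the single highest value is not enough, because the axillary value is lost whenever the rectal one is higher.
- **SAP 6.3.2:** keep the planned fever table. Add a supportive tabulation on axillary readings only, and the number of infants with a rectal re-measurement by group.
- **Diaries already collected without route:** state the limitation in the study report; it cannot be repaired at analysis.

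The cost is a second temperature entry in the eDiary, a clarifying sentence and one extra table. Parents already receive both thermometers (8.10.5) and instruction on both routes (8.10.2). No fever threshold or clinical rule is proposed.
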